2.0 Goals

2.1 Primary Goal

2.1.1 To assess the feasibility and safety of Y90-RE combined with immunotherapy durvalumab to treat liver-predominant mCRC.

2.2 Secondary Goals*

2.2.1 To report **treatment related adverse events** in patients treated with the combination treatment of Y90-RE and durvalumab as assessed by Common Toxicity Criteria for Adverse Events (CTCAE) version 5.0

2.2.2 To determine the **Recommended Phase II dose (RP2D)** of durvalumab in combination with Y90-RE to treat liver-predominant mCRC.

2.2.3 To determine the efficacy of combination treatment of Y90-RE and durvalumab in patients with liver-predominant mCRC measured by overall response rate (**ORR**) (complete response (CR) + partial response (PR)) post-Y90-RE and immunotherapy.

2.2.4 To determine the efficacy of combination treatment of Y90-RE and durvalumab in patients with liver-predominant mCRC measured by the disease control rate (**DCR**) (CR+PR+stable disease (SD)) at 2 months post-Y90-RE treatment.

2.2.5 To determine the efficacy of the regimen in the treated liver metastases (liver-specific progression free survival (**Liver-PFS**) in the lesions in the Y90-RE field).

2.2.6 To determine the efficacy of the regimen in the patient as a whole (**PFS**); including both Y90-RE field and outside the Y90-RE field.

- 2.2.7 To determine the efficacy of combination treatment of Y90-RE and durvalumab in subject with liver-predominant mCRC as measured by overall survival (**OS**) at 1-year and 2-year.
- 2.2.8 To determine duration of response (**DOR**) in the Y90-RE field and outside of Y90-RE field
 - * *Given Y90-RE to the liver and use of immunotherapy, all response assessments by modified RECIST (mRECIST) as well as immune RECIST (iRECIST). In all instances, the landmark time is the initiation of immunotherapy.*

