7. Gross (dipstick) urine examination: Leukocytes, nitrite, pH, protein, glucose, ketone, urobilinogen, bilirubin, blood (hemoglobin and erythrocytes). If abnormalities are detected by dipstick, then a microscopic sediment test should also be performed. If a UTI is suspected, it can be treated.
8. Durvalumab administration over 60 minutes. Following infusion, subjects must be observed for 30 minutes post infusion for potential infusion related reactions. The number of doses administered is per dose level for each patient cohort.
9. The 2nd durvalumab dose can be done \leq 5 days prior to Y90-RE or same day as long as it is before the Y90-RE.
10. Blood biomarkers will be collected in the morning of visit. Kits are required.
11. Tissue specimens must be collected the following timepoints: pre-treatment [screening/prior to cycle 1 of Durvalumab (fresh as well as archived if available)], and post-treatment. Kits are required (banking, clinical as well as real-time send out).
12. Visit will occur 8 weeks after Y90-RE.
13. Clinical follow-up visits will be performed at least every 3 months (or as per standard physician practice) for 2 years.
14. Cohort 1- Durvalumab given at cycle 1 and cycle 2 only
15. Cohort 2- Durvalumab given at cycle 1, 2, and 4
16. Dose escalation cohort- Durvalumab given cycle 1, 2, 4 and 5
17. Dose expansion cohort- Durvalumab given cycle 1, 2, 3, 4, and 5
18. As long as the lesion is amenable to a biopsy and is done, the biopsy can be done on the Tc-99m labelled MAA eligibility mapping day to save patient a visit. Has to be prior to anti-PD1 therapy though. From a safety perspective since we need to know about the shunting to other organs prior to the Y90-RE, the mapping can be done during the screening or even prior to considerations for this study if already performed within 12 months of intended Y90-RE, it would not need to be repeated unless as per interventional radiology. Biopsy still needs to be done as noted.
19. If there is complete response of the lesion in the field of Y90-RE, tissue biopsy of the field would still be done to assess for the immune changes and an alternative tumor lesion can be biopsied for testing of the tumor itself.
20. At the time of progression, patient would be approached for a tissue biopsy and research blood sampling similar to the end of treatment visit.

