7.1.2 Treatment table for Y-90 Radioembolization (Y90-RE)

Agent	ReRx
TheraSpheres™	Per Table 1 section 7.4.1

Cycle= 14 days

Note: Y90-RE is administered 2 weeks post first durvalumab dose administration with cycle 2 of Durvalumab. The immunotherapy dose is prior to the Y90-RE. The immunotherapy does not have to be the same day as long as it is prior to Y90-RE.

Note: The Y90-RE dose and administration will be as per the FDA approved USPI for each patient. Goal is to deliver an ablative radiation dose to the targeted region and trigger a release of neo-antigens in order to augment immunotherapy; all the while minimizing collateral damage by sparing normal liver parenchyma. Per package insert, recommended Y90-RE dose is 80 Gy to 150 Gy per lobe of liver; this is intended to prevent radioembolization-induced liver disease (REILD). Upper limit for dose administration is also determined by the lungs, which may receive an estimated dose of no more than 30 Gy from a single administration nor a cumulative total of 50 Gy from multiple administrations.

As noted in the protocol, there are numerous dosing methods in place for Durvalumab.

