11.1 Treatment evaluation using mRECIST as well as iRECIST Guidelines

The first scan prior to treatment initiation will be performed; the next scan will be then performed at the end of treatment visit. It will then continue every 8-12 weeks per physician discretion until disease progression is confirmed or withdrawn of consent. (See Section 4.0).

Disease progression for this protocol is defined as meeting the mRECIST as well as iRECIST criteria detailed in appendix VI.

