A.5 Evaluation of best overall response

The best overall response is the best response recorded from the start of the treatment until disease progression/recurrence (taking as reference for PD the smallest measurements recorded since the treatment started). In general, the patient's best response assignment will depend on the achievement of both measurement and confirmation criteria

Target lesions	Non-Target lesions	New Lesions	Overall response
CR	CR	No	CR
CR	Incomplete response/SD	No	PR
PR	Non-PD	No	PR
SD	Non-PD	No	SD
PD	Any	Yes or No	PD
Any	PD	Yes or No	PD
Any	Any	Yes	PD

- Patients with a global deterioration of health status requiring discontinuation of treatment without objective evidence of disease progression at that time should be classified as having “symptomatic deterioration”. Every effort should be made to document the objective progression even after discontinuation of treatment.
- In some circumstances it may be difficult to distinguish residual disease from normal tissue. When the evaluation of complete response depends on this determination, it is recommended that the residual lesion be investigated (fine needle aspirate/biopsy) to confirm the complete response status.

A.6 Confirmation

- The main goal of confirmation of objective response is to avoid overestimating the response rate observed. In cases where confirmation of response is not feasible, it should be made clear when reporting the outcome of such studies that the responses are not confirmed.
- To be assigned a status of PR or CR, changes in tumor measurements must be confirmed by repeat assessments that should be performed no less than 4 weeks after the criteria for response are first met. Longer intervals as determined by the study protocol may also be appropriate.
- In the case of SD, follow-up measurements must have met the SD criteria at least once after study entry at a minimum interval (in general, not less than 6-8 weeks) that is defined in the study protocol

A.7 Duration of overall response

- The duration of overall response is measured from the time measurement criteria are met for CR or PR (whichever status is recorded first) until the first date that recurrence or PD is objectively documented, taking as reference for PD the smallest measurements recorded since the treatment started.
- Duration of stable disease

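### Read literally, the section 2.2 footnote starts duration of response at the first durvalumab dose; Appendix IV.A A.7 starts it at first documented response, and section 17.5 does not say which applies

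*Combined protocol and SAP*

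**What the plan says.** The asterisk on the heading of section 2.2 leads to a footnote below goals 2.2.1 to 2.2.8. After naming mRECIST and iRECIST for response assessment, the footnote adds: "In all instances, the landmark time is the initiation of immunotherapy". The last goal on the list, 2.2.8, reads: "To determine duration of response (DOR) in the Y90-RE field and outside of Y90-RE field". The footnote makes no exception for it.

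Appendix IV.A, A.7 gives a different start: "The duration of overall response is measured from the time measurement criteria are met for CR or PR", taking whichever of the two is recorded first. The end is the first objectively documented recurrence or progression.

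Section 17.5 has paragraphs on adverse events, toxicity, overall response rate, disease control rate, overall survival and laboratory correlates. It has none on DOR, PFS or Liver-PFS. The overall survival paragraph, 17.5.5, counts from randomization, although 17.1 describes a single-arm study.

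On scan timing, section 11.1 says that after the pre-treatment scan "the next scan will be then performed at the end of treatment visit". Footnote 12 of the test schedule in 4.1 places that visit: "Visit will occur 8 weeks after Y90-RE".

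**The concern.** DOR is meant to show how long a response lasts once it exists. If the clock starts at the first dose, the result is time from treatment start to progression among responders, which is in effect PFS or Liver-PFS restricted to patients who responded. Goal 2.2.8 would then no longer measure what its name says.

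Two analysts working from the same data, one following the footnote and the other A.7, would report different durations, and nothing in 17.5 tells them which to use. The difference is systematic and always in the direction of longer DOR. Section 17.3 says that the collected data, tumor response among them, will inform a subsequent Phase II trial, so a reader of the results could take the pre-response interval for durability.

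**Working it through.** The plan states no figure for DOR, so there is none to reproduce. The check is a timeline built from the protocol's own schedule.

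**Inputs**

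- First durvalumab dose to Y90-RE, levels 1 to 4: 2 weeks = 14 days. Section 7.1.2: "Y90-RE is administered 2 weeks post first durvalumab dose administration with cycle 2 of Durvalumab".
- Y90-RE to the end-of-treatment visit, where the first post-baseline scan is scheduled: 8 weeks = 56 days (4.1 footnote 12; 11.1).
- Visit windows: ±5 days at cycle 2 and at end of treatment (4.1).
- The second durvalumab dose may precede Y90-RE by up to 5 days (4.1 footnote 9).
- Later scans, 11.1: "It will then continue every 8-12 weeks per physician discretion".
- First durvalumab dose at level -1: week 4 after Y90-RE; at level -2: week 6 (Table 1 in 1.4.6). The grids in 7.4.1 and 17.2 do not line up with Table 1 in the text available to me, possibly because columns shifted on extraction, so I use Table 1.

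**Formula.** Both clocks stop at progression, so:

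DOR (footnote) − DOR (A.7) = date response is first documented − date of first durvalumab dose.

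**Levels 1 to 4, response first seen at the end-of-treatment scan**

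- Nominal: 14 + 56 = 70 days = 10 weeks.
- Both windows early: (14 − 5) + (56 − 5) = 60 days. If the two-week minimum between doses in 7.1.1 is enforced: 14 + 51 = 65 days.
- Both windows late: (14 + 5) + (56 + 5) = 80 days.
- Both windows late, with Y90-RE 5 days after the second dose: 80 + 5 = 85 days.

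**Levels 1 to 4, response first seen one scan later.** The addition grows to 10 + 8 = 18 weeks up to 10 + 12 = 22 weeks. For scheduled scans, 10 weeks is therefore the nominal minimum.

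**Levels -1 and -2, response first seen at the end-of-treatment scan**

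- Level -1: 8 − 4 = 4 weeks.
- Level -2: 8 − 6 = 2 weeks.

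**Example.** Response at the end-of-treatment scan, progression at the next scan, levels 1 to 4:

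| Interval to next scan | DOR under A.7 | DOR under footnote | Ratio |
|---|---|---|---|
| 8 weeks | 8 weeks | 8 + 10 = 18 weeks | 18/8 = 2.25 |
| 12 weeks | 12 weeks | 12 + 10 = 22 weeks | 22/12 = 1.83 |

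For the same patient the footnote would give 12 to 16 weeks at level -1 and 10 to 14 weeks at level -2.

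**The case against.** The best defence is that the footnote is a loosely worded general remark. It speaks of a landmark time, directly after a sentence on response assessment, and never says that DOR is computed from first dose to progression. The protocol already departs from it: response rate and disease control rate are assessed 2 months after Y90-RE, and overall survival runs from randomization. A specific definition such as A.7 can reasonably be held to override a general remark, and 17.5.3 relies on the same appendix (A.9) for reporting. On that view no careful analyst would compute DOR from the first dose.

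This shows that a sensible reading exists. It does not show that the plan has chosen it. The footnote is attached to a list that contains DOR and admits no exception. A.7 belongs to a generic RECIST quick reference, while response here is assessed by mRECIST and iRECIST, so its authority over this endpoint is not beyond dispute. It is nevertheless the only DOR rule written as guidance for this trial. The package insert in Appendix VI reports older studies that counted response duration from the TheraSphere date, but that describes other studies and matches neither rule.

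Several stronger readings might be inferred, and the documents do not support them:

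- *Every clock in the trial starts at the first dose.* The footnote says so, but response rate, disease control rate and overall survival are anchored elsewhere.
- *Every responder gains the same 70 days.* The addition varies with the visit windows, the scan at which response is first seen and the dose level. An unscheduled earlier scan is not forbidden and would shorten it.
- *DOR is overstated by a known percentage.* The documents give no expected DOR, so any such percentage rests on an outside assumption.
- *The dose levels will not be comparable.* Levels -1 and -2 open only if level 1 meets its stopping boundary, and 17.3 does not expect DLTs.
- *The trial's main conclusions are at risk.* The primary goal is feasibility and safety, the expansion cohort's primary objective is immune-cell change, and 17.5 treats all results as exploratory.

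**Conclusion.** The contradiction between the 2.2 footnote and A.7 is real, and 17.5 leaves it open. Followed literally, the footnote lengthens DOR at the starting and escalation levels by nominally at least 10 weeks, enough to roughly double it for a patient who progresses at the first follow-up scan. This rests on the scheduled scan times being kept and, for the de-escalation levels, on Table 1 being the correct grid.

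The consequence is confined to one descriptive secondary endpoint, estimated only among the responders in a trial planned for 18 patients. A first-dose start is a usual choice for PFS and OS in a single-arm trial; the fault lies in extending it to DOR. The point should be corrected before analysis, but it does not affect the trial's design.

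**What to change.** Three edits, made together so that no conflict remains:

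1. **Section 2.2 footnote.** Restrict the time-zero statement to PFS, Liver-PFS and OS, with time zero the first durvalumab dose.
2. **Section 17.5.** Add a DOR paragraph: DOR, in the Y90-RE field and outside it, runs from the first scan meeting CR or PR criteria to documented progression. State how death without documented progression is handled, since A.7 does not say.
3. **Section 17.5.5.** Replace randomization with the first durvalumab dose. Without this edit, the revised footnote and 17.5.5 would still give two different starts for overall survival.

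The cost is a few sentences. No scan, visit or data item changes. The downside for the sponsor is that reported DOR will be shorter than under the footnote clock.

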2.3 Correlative Research

- 2.3.1 To assess the changes in immune infiltration (TISSUE: tumor-infiltrating lymphocytes – **TILs (CD-3, CD-8), PD-L1 and PD-1 expression**, pre- and post-Y90-RE and immunotherapy).
- 2.3.2 To analyze serial changes in **immune cells** (BLOOD) pre- and post-Y90-RE and immunotherapy
- 2.3.3 To determine changes in the expression profile and in levels of circulating tumor DNA (**ctDNA**) in blood pre- and post- treatment.
- 2.3.4 To evaluate **mutation burden** by whole-exome sequencing pre- and post-treatment (TISSUE)
- 2.3.5 To evaluate concomitant expression profile changes through **RNA-Seq** pre- and post-treatment (TISSUE)
- 2.3.6 To evaluate the **feasibility** of developing patient derived organoids, xenografts and/or cell-lines at the time of pre- and post-treatment biopsies
- 2.3.7 Correlation of outcomes based on **subtypes** of mCRC (sidedness, mutational/molecular subtypes)
- 2.3.8 To report on any *abscopal effects* seen in terms of responses outside the Y90-RE field.

3.0 Registration Patient Eligibility

Prior to discussing protocol entry with the patient, call the GI clinical trial coordinator or PI for dose level and to ensure that a place on the protocol is open to the patient.

3.1 Inclusion Criteria

- 3.1.1 Age \geq 18 years
- 3.1.2 Histological or cytological confirmation of colorectal cancer with metastasis to the liver. Mismatch repair or microsatellite instability status of the tumor needs to be known. Tumors need to be mismatch repair proficient (for mismatch repair deficient tumors immunotherapy is already approved).
- 3.1.3 Patient must have at least 1 liver lesion measurable as defined in [Section 11.0](#).
- 3.1.4 Must have liver metastases and be appropriate for treatment with Y90-RE therapy as determined by the treating medical oncologist and interventional radiologist/oncologist, and nuclear medicine physician(s).

NOTE: the goal of therapy is safety and parenchymal sparing. Typically, since the treatment is personalized, the goal is to have at least 30% liver parenchymal sparing post treatment.

- 3.1.5 Must have a metastatic focus amendable to biopsy. It is permissible to use same or alternative lesion for biopsy for assessment for tumor response and changes in microenvironment (mandatory pre- and post-Y90-RE biopsy).
- 3.1.6 **At least 2 but no more than 3 lines of therapy** allowed in metastatic setting. These include at least treatment with a fluoropyrimidine, oxaliplatin, and/or irinotecan-based

therapy and an anti-EGFR therapy if RAS wild-type (unless deemed intolerant or not suitable by the treating oncologist), with or without an anti-VEGF therapy.

NOTE: adjuvant and/or maintenance chemotherapy does not count as an additional line of therapy. (Patients with more than 3 lines of therapy are at risk for liver disease from prior systemic therapies and would not be reasonable candidates for Y90-RE).

- 3.1.7 At least a 4-week gap between anti-VEGF therapy and the IR Tc-99m labelled MAA eligibility mapping
- 3.1.8 ECOG Performance Status (PS) 0 or 1 ([Appendix I](#)).
- 3.1.9 Negative *serum* pregnancy test done ≤ 7 days prior to registration, for persons of childbearing potential only.
- 3.1.10 Females of childbearing potential (FOCBP), must use appropriate method(s) of contraception. FOCBP are defined as those who are not surgically sterile (i.e., bilateral tubal ligation, bilateral oophorectomy, or complete hysterectomy) or postmenopausal (defined as 12 months with no menses without an alternative medical cause). Additionally, FOCBP must agree to follow instructions for method(s) of contraception for the duration of treatment with durvalumab plus 5 half-lives of durvalumab (13 weeks) plus 30 days (duration of ovulatory cycle) for a total of 17 weeks post-treatment completion (details in appendix).
- 3.1.11 Men who are sexually active with FOCBP must agree to follow instructions for method(s) of contraception for the duration of treatment with durvalumab plus 5 half-lives of durvalumab plus 90 days (duration of sperm turnover) for a total of 25 weeks post-treatment completion (details in appendix).
- 3.1.12 Provide written informed consent.
- 3.1.13 Ability to complete questionnaire(s) by themselves or with assistance.
- 3.1.14 Willingness to provide mandatory blood specimens for correlative research (see Section 14.0).
- 3.1.15 Willingness to provide mandatory tissue specimens for correlative research (see Section 17.0). **NOTE:** If tissue is deemed inaccessible, patient cannot participate in study.
- 3.1.16 Willingness to return to enrolling institution for follow-up (during the Active Monitoring Phase of the study).
- 3.1.17 Must have a life expectancy of at least 6 months.

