4.0 Test Schedule

4.1 Test schedule for metastatic CRC

Tests and procedures	Screening		Active Monitoring Phase					
	Reg	Cycle 1	Cycle 2 (2 nd dose of Durva + Y90-RE)*	Cycle 3	Cycle 4	Cycle 5	End of treatment visit ¹²	Clinical Follow-up ¹³ (every 3 months)
Window	21 days	±5 days	±5 days	±5 days	±5 days	±5 days	±5 days	
History and exam ³ , Wt ⁵ , BP, HR, ECOG PS	X							
Exam, Wt ⁵ , BP, HR, ECOG PS		X	X	X	X	X	X	X
Adverse event assessment	X	X	X	X	X	X	X	X
Concomitant medication review	X	X	X	X	X	X	X	X
Height	X							
IR Consult	X							
Pregnancy test ¹	X		X		X		X	X
Hematology group CBC w/ 5-part differential	X	X	X	X	X	X	X	X
Chemistries ²¹	X	X	X	X	X	X	X	X
Thyroid Function Test TSH, free T4, amylase, lipase, Vitamin D	X		X		X		X	X
Creatinine clearance	X	X	X	X	X	X	X	X
Coagulation PT, PTT, INR	X						X	
Cholesterol, triglycerides	X							
IR Tc-99m labelled MAA eligibility mapping		X ¹⁸						
Tumor measurement ²	X						X	X
ECG ⁶	X		X		X		X	
Urinalysis ⁷	X	X	X	X	X	X	X	X
Administer durvalumab ^{8,R}		X ^{16,17,18,19}	X ^{9,16,17,18,19}	X ¹⁹	X ^{17,18,19}	X ^{17,18,19}		
Administer Y90-RE			X					
Patient Questionnaire Booklets ⁴ (Appendix III)		X	X	X	X	X	X	
Mandatory Research Specimens (see companion Lab Manual) ^{10,R}	X	X ^{14,15,16,17}	X ^{14,15,16,17}	X ¹⁷	X ^{15,16,17}	X ^{15,16,17}	X	
Mandatory Research Tissue specimens (see companion Lab Manual) 11,R	X (Pre- treatment) ₁₈						X (Post- treatment) _{19, 20}	

Cycle = 14 days

1. For women of childbearing potential only. Serum pregnancy test. Must be done \leq 7 days prior to registration.
2. A scan is required at baseline prior to the first dose of durvalumab. The scan does not need to be repeated as long as it is \leq 28 days prior to registration. Preferably we would recommend a CT of the chest and pelvis; and an MRI of the abdomen for assessment of liver metastases. If an MRI cannot be performed, a CT chest, abdomen, and pelvis would be acceptable. Please use same imaging throughout the study.
3. History and exam include prior surgery, cancer-related and other treatment and known positivity for Hepatitis B surface antigen, Hepatitis C virus antibodies, and Human Immunodeficiency Virus antibodies 1 /-2.
4. Patient questionnaire booklets **must** be used; copies are not acceptable for this submission
5. Body weight to be measured within 72 hours prior to durvalumab administration.
6. Single 12-lead ECG after 5 min rest in supine position.

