11.0 Treatment Evaluation/Measurement of Effect

Various measurement options exist that are being done in patients with liver cancer and liver metastases and immunotherapy that are of value to consider. These include:

- RECIST 1.1
- iRECIST
- mRECIST

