11.2 Definitions of measurable and non-measurable disease

11.21 Target Lesion Response mRECIST

- **Complete Response** - Disappearance of any intratumoral arterial enhancement in all target lesions.
- **Partial Response** - At least a 30% decrease in the sum of the diameters of viable (enhancement in the arterial phase) target lesions, taking as reference the baseline sum of the diameters of target lesions.
- **Progressive Disease** – An increase of at least 20% in the sum of the diameters of viable (enhancing) target lesions, taking as reference the smallest sum of the diameters of viable (enhancing) target lesions recorded since treatment started.
- **Stable Disease** – Any cases that do not qualify for either partial response or progressive disease.

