17.5.3 Overall Response Rate

Overall response rate is defined as the proportion of evaluable patients that have achieved a complete response or partial response using mRECIST evaluation criteria. ORR will be evaluated at 2 months post-Y90RE treatment (\pm 5 business days).

ORR will be analyzed descriptively as a point estimate with a 95% confidence interval.

Results will be reported consistent with RECIST v1.1 (Appendix A.9).

An “evaluable subject” for the purpose of evaluation of the combinatorial therapy is one who receives both Y90-radioembolization and at least 1 dose of durvalumab.

Subjects who do not receive Y90-RE or received only a single incomplete dose of immunotherapy (i.e., allergic reaction), are considered non-evaluable for assessment of efficacy. These subjects would be replaced for the proposed sample size of 18.

All subjects included in the study must be assessed for response to treatment, even if there are major protocol treatment deviations or if they are ineligible.

Each subject will be assigned one of the following categories: 1) complete response (mRECIST), 2) partial response (mRECIST), 3) stable disease (mRECIST), 4) progressive disease (mRECIST), 5) early death from malignant disease, 6) early death from toxicity, 7) early death because of other cause, or 9) unknown (not assessable, insufficient data).

Category 4 (protocol specific definition): includes clinical progression as determined by the principal investigator and confirmed by the independent data and safety monitoring committee (DSMC).

Category 5 (protocol specific definition): death from malignant disease as determined by the principal investigator and confirmed by the independent data and safety monitoring committee (DSMC).

Category 6 (protocol specific definition): death from toxicity as determined by the principal investigator and confirmed by the independent data and safety monitoring committee (DSMC).

Category 7 (protocol specific definition): includes death not meeting categories 5 or 6, or death defined as not otherwise specified.

Category 9 (protocol specific definition): includes subjects who did not receive radioembolization, or who did not receive at least 1 complete infusion of durvalumab, or who did not undergo follow-up imaging (other than for clinical progression, toxicity, or death), or subjects who are lost to follow-up.

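### The mRECIST partial-response rule sets enhancing tumour at follow-up against a baseline sum not limited to enhancing tumour, so read literally an unchanged patient can score PR.

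*Combined protocol and SAP*

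**What the plan says.** Section 17.5.3 defines ORR as the proportion of evaluable patients with "complete response or partial response using mRECIST evaluation criteria", assessed 2 months after Y90-RE.

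Section 11.21 sets the mRECIST target-lesion rules. PR is "At least a 30% decrease in the sum of the diameters of viable (enhancement in the arterial phase) target lesions", and the reference for that decrease is the baseline sum of target-lesion diameters with no restriction to viable tissue. The full comparison reads "viable (enhancement in the arterial phase) target lesions, taking as reference the baseline sum of the diameters of target lesions". The PD rule in the same list limits both the follow-up sum and its reference (the smallest sum since treatment started) to viable diameters. CR is "Disappearance of any intratumoral arterial enhancement in all target lesions". Appendix IV.C repeats the same PR and PD references.

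Eligibility 3.1.3 reads "Patient must have at least 1 liver lesion measurable as defined in" Section 11.0. That section opens with "Various measurement options exist that are being done in patients with liver cancer and liver metastases and immunotherapy that are of value to consider" and lists RECIST 1.1, iRECIST and mRECIST. Section 11.2 is headed "Definitions of measurable and non-measurable disease", but only response categories, new-lesion rules and HCC notes follow. Size rules for measurable lesions appear only in Appendix IV.A (at least 20 mm, or at least 10 mm on spiral CT) and IV.B (at least 10 mm). Neither mentions enhancement, and 3.1.3 cites neither. Appendix IV.C has no measurability rule.

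On imaging, footnote 2 to Section 4.1 says "Preferably we would recommend a CT of the chest and pelvis; and an MRI of the abdomen for assessment of liver metastases", accepts CT if MRI cannot be done, and asks for no arterial phase.

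**The concern.** A percentage change is interpretable only if the same quantity is measured at both times. As worded, PR subtracts an enhancing diameter at follow-up from a sum that may include non-enhancing tumour at baseline. Any tissue that was already non-enhancing before treatment is then counted as shrinkage.

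The patients are pretreated (two to three prior lines under 3.1.6), and nothing in the plan requires a target lesion to enhance at baseline. If the literal reading is applied, ORR is biased upward by patients in whom nothing has happened. Section 17.3 says tumour response is among the data that will inform a subsequent Phase II trial, so an inflated ORR would be carried forward. Without an arterial phase at baseline the viable sum cannot be rebuilt later.

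**Working it through.** The plan states no figure on this point, so there is none to reproduce. The check applies the written rules to lesions with known change.

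**Inputs.** PR threshold 30% and PD threshold 20% (11.21). Baseline sum as total longest diameter of all target lesions (Appendix IV.A, A.3, the only construction rule given). n=18 (17.5.3). The lesion sizes are illustrations.

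**Notation.** T = baseline total diameter sum; V0 = baseline viable sum; V1 = follow-up viable sum.

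**Step 1: unchanged disease (V1 = V0), literal reading.** Apparent decrease = (T − V1)/T. With T = 50 mm:

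| Enhancing share V0/T | V1 (mm) | Apparent decrease | Category |
|---|---|---|---|
| 100% | 50 | 0% | SD |
| 80% | 40 | 20% | SD |
| 71% | 35.5 | 29% | SD |
| 70% | 35 | 30% | PR |
| 60% | 30 | (50 − 30)/50 = 40% | PR |

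The break-even is V0/T = 1 − 0.30 = 70%. Two unchanged targets, one of 30 mm fully enhancing and one of 20 mm not enhancing, also give (50 − 30)/50 = 40%. At a 60% enhancing share the viable part can grow from 30 to 35 mm (35/30 − 1 = 16.7%) and still meet PR.

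**Step 2: one scan meeting both rules.** Take T = 50, V0 = 25, V1 = 31. The end-of-treatment scan is the first after baseline (11.1), so the smallest viable sum to date is V0.
- PD: 31/25 − 1 = +24%, which meets 20%.
- PR: (50 − 31)/50 = 38%, which meets 30%.

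In general both are met when 1.2 × V0 ≤ V1 ≤ 0.7 × T, which is possible once V0/T ≤ 0.70/1.20 = 58.3%. No tie-break is given. The table in A.5 combines target, non-target and new-lesion categories; it does not choose between two categories for the same target lesions.

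**Step 3: the same cases with a viable baseline reference.** Change = (V0 − V1)/V0. Every unchanged enhancing lesion in Step 1 gives 0%, so SD. The Step 2 case gives −24%, so PD only. A lesion with V0 = 0 has a zero denominator, so its change is undefined and a separate rule is needed.

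**Step 4: size at n=18.** Each patient wrongly moved to PR adds 1/18 = 5.6 points. Exact (Clopper-Pearson) 95% intervals:
- 0/18 = 0% (0 to 18.5)
- 1/18 = 5.6% (0.1 to 27.3)
- 2/18 = 11.1% (1.4 to 34.7)
- 3/18 = 16.7% (3.6 to 41.4)

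The share q of patients at or below a 70% enhancing fraction is not in the documents. For assumed q of 5%, 10%, 20% and 30%, the expected number is 18q = 0.9, 1.8, 3.6 and 5.4, and the chance of at least one, 1 − (1 − q)^18, is 60%, 85%, 98% and over 99%.

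**The case against.** The strongest reply is that the rule asks for a decrease in the viable sum, so both sides must be viable. On that reading 30 mm to 30 mm is no decrease, and the baseline sum is simply the earlier value of the same quantity. The wording also matches Appendix IV.C, which is presented as adapted from the published mRECIST paper. This reading is available, and it is probably how an experienced reader would score. It does not settle the matter: the same list limits the PD reference to viable tissue and leaves the PR reference open, and A.3 points to total diameter.

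Second, the iRECIST read is planned alongside (Sections 2.2, 11.1 and 17.5.2). A spurious mRECIST PR would sit beside a size-based SD and be visible. That stands, but 17.5.3 still defines ORR by mRECIST.

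Third, ORR is a secondary goal, analysed descriptively with no threshold or hypothesis, and Section 17.5 calls all results exploratory. That stands and limits the severity.

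Fourth, patients must be judged suitable for Y90-RE by several specialties (3.1.4), and the background describes the treatment as relying on tumour hypervascularity. This does not exclude poorly enhancing lesions, but it is a reason not to assume that they are common.

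**Conclusion.** The PR reference in 11.21 and IV.C is ambiguous. On its literal reading it gives PR to unchanged patients with an enhancing share of 70% or less, and can assign PR and PD to one scan. The size is 5.6 points of ORR per affected patient at n=18, for a patient who would not otherwise respond. The number affected is unknown, and the range in Step 4 is an assumption. This should be fixed, but it does not threaten the trial's primary purpose.

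Four stronger conclusions that a reader might infer are not supported:
- *DCR is inflated too.* An unchanged patient is SD and already counts, so a move to PR leaves DCR the same. Among the cases worked here, DCR depends on the choice of rule only where PR and PD conflict.
- *Never-enhancing lesions score CR.* A follow-up viable sum of zero meets the PR threshold arithmetically, but CR holds only if disappearance is read as absence. Enhancement that was never present arguably cannot disappear, and the plan does not decide this.
- *The inflated ORR would be judged against the 0 of 18 responses in Section 1.1.* That figure is PD-1 blockade alone, and no comparison with it is planned.
- *Eligibility itself is wrong, or safety conclusions are affected.* The bias arises in 11.21, and changing 3.1.3 would leave it there. DLT and MTD rules and the immune-change basis for n=18 do not use response.

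**What to change.** 1. In 11.21 and Appendix IV.C, make the PR reference the baseline sum of viable (arterially enhancing) diameters, matching the PD rule.
2. In Section 11.2, where 3.1.3 already leads, add a definition: an mRECIST target lesion meets the size rule (state which of the two in Appendix IV applies) and has a measurable enhancing part on the baseline arterial phase. Add that patients without such a lesion stay eligible, are not counted as mRECIST CR or PR, and are described by the iRECIST read already planned. They remain in the ORR denominator, because 17.5.3 defines evaluable by treatment received.
3. In footnote 2 to Section 4.1, state that the baseline and end-of-treatment liver scans include an arterial phase. The footnote already asks for the same imaging throughout, so later scans follow.

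Enhancement should not become an entry criterion; that would narrow an 18-patient phase I trial without being needed to correct the endpoint.

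The cost is protocol wording and a contrast-phase setting on scans already scheduled. The downside is that the reported mRECIST ORR may be lower and a few patients will have only a size-based response. The imaging change has to be in place before baseline scans are taken, since a missing arterial phase cannot be recovered.
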